We will use the radiotracer [11C]DASB to measure serotonin (5-HT) transporter binding and [11C]CUMI-101 to measure serotonin receptors in the brain of depressed or recently depressed bipolar subjects using Positron Emission Tomography (PET) before and after treatment with a mood stabilizer. We propose to assess how the clinical responses to two types of mood stabilizer treatment relate to the state of the serotonin system. The two treatments we intend to compare are lithium and lamotrigine. We propose to perform [11C]CUMI-101 and [11C]DASB in 38 medication free bipolar subjects during a major depressive episode and compare 5-HTT and 5-HT_{1A} binding potential in 38 healthy volunteers. We will also examine the diagnostic specificity of lithium response by studying 10 unipolar depressed subjects in an identical manner.

We will obtain blood samples from all subjects in the protocol in order to be able to evaluate their genetic information. We plan to analyze the DNA from the blood to assess for genome wide and single nucleotide polymorphisms and their associations with MRI and PET brain imaging measures. For example, the effects of the C(-1019)G 5-HT1A promoter polymorphism has been shown to affect the binding of our 5-HT1A tracers in humans. The genetic information may also be used to study the general pathophysiology of major depression, bipolar disorder or past suicidal ideation in the subjects. Blood RNA will also be evaluated because it tells us whether the gene variants are associated with altered gene expression. We expect gene variants with altered expression levels to be of greater pathophysiological consequence.

2. Research Site

Stony Brook University Human Subjects Committee (IRB) PSF 2/23/15

Page 9 of 37

IRB# 2012-1826-F PI: [name]

MRI scans, research interviews, clinical assessments and treatment will take place at Stony Brook University Medical Center. PET scans will take place at the Yale University PET Center in New Haven, CT.

3. Study Sample

86 subjects in total are proposed. The power calculations are below.

Age range: 18-70

Total subjects: N = 86 (38 bipolar, 38 healthy volunteer, 10 unipolar)

Gender: Male and female representation are about equal.

No ethnic/racial/gender group is excluded.

4. Screening

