PET experiments will be conducted at the Yale University PET Center, [name], in New Haven, CT. [11C]CUMI-101 and [11C]DASB scans will be performed. Participants may have only one of these scans, depending on radiotracer availability. The PET scans will preferably be performed after the MRI scan, but the order may be reversed if needed.

Participants will be provided with transportation from Stony Brook University to Yale University by a combination of taxi/car service, ferry, and/or train. Participants will be accompanied by a staff member while traveling to/from Yale University. Participants will arrive the night before the scheduled scan day(s) and be given accommodations at a nearby hotel at no cost to them.

On the day of the scans, a urine pregnancy test will be done on females to ensure that pregnancy has not occurred between the time of the screening and the PET scans. All participants will also have a urine drug screen. The preparation of the subject will include the placement of one venous lines (for radiotracer injection), a second venous line (for and blood sampling), and an arterial line (for blood sampling). An experienced physician will place the arterial line after infiltration of the skin with 1% lidocaine. A transmission scan is then obtained. Before injection of the radiotracer, approximately 8ml of venous blood will be collected. For the [¹¹C]CUMI-101 scan, up to 20 mCi of [¹¹C]CUMI-101 (mass dose of 5 µg or less) will be administered i.v. after the transmission scan. Emission data will be collected for up to 120 minutes. At the time of injection, arterial sampling will be initiated. In order to demonstrate that the arterial and venous metabolites are the same for late time points, a 4 mL venous sample will be initiated at 60 and 90 minutes. 90 ml or less will be collected during scan time.

At the end of the scan, subjects will be provided with a light meal and be allowed to relax. For the [\frac{11}{C}]DASB scan, the subject will go back on the scanner table and an injection of up to 20 mCi of [\frac{11}{C}]DASB, (mass dose of 10 \mug or less) will be administered. Emission scan and arterial sampling will be resumed as described above. A 4 mL venous sample will be initiated at 50 and 80 minutes. Thus, maximal blood sampling during the entire PET procedure will be approximately 180 ml (about 12 tablespoons).

IRB# 2012-1826-F PI: [name] Stony Brook University Human Subjects Committee (IRB) PSF 2/23/15

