To assess the impact of lithium on the neuroreceptor measures we conservatively use the higher test/retest variability of the [¹¹C]DASB compound and assume a 20-25% change in both 5-HT_{1A} and 5-HTT after chronic lithium based on preclinical data. ¹4,16-18 Assuming 50% of the subjects complete the lithium treatment and repeat scans and this degree of change, we have a power of between 79% and 90% as this is a paired analysis. Estimated outcome measures will be analyzed for all ROIs and all patients in a linear mixed model with patient as random effect and ROI and remission status as fixed effects. Our previous studies have demonstrated that the standard deviation of BP across patients increases approximately linearly with the mean of the region, and so the BP values are first log-transformed in order to satisfy the assumptions of the modeling (constant variance across regions). For the pre/post imaging of the non-remitters, a linear mixed model will again be used with ROI and condition (before/after) as fixed effects and with two levels of random effects -- a patient effect and a study within patient effect. Many potential covariates will also be measured for each patient and will be included in the model when appropriate. Modeling will be done using R software (www.r-project.org).

F. Funding Status, Details

The study is currently funded through the National Institutes of Health (NIH) through May 31, 2017. Grant Title: Lithium's Molecular Mechanism of Action and the Pathology of Bipolar Disorder

G. Human Subjects Research Protection from Risk

1. Risk to Subjects and 2. Adequacy of Protection Against Risks

Risks associated with participation in this study are related to 1) Drug-free interval; 2) placement of intraarterial catheter; 3) blood sampling; 4) discomfort during scanning (PET and MRI); 5) MRI scan; 6) radiation exposure; 7) toxicology (idiosyncratic reaction to the tracer); 8) genetic testing/confidentiality; 9) pregnancy and 10) risks associated with lithium/lamotrigine use.

Stony Brook University Human Subjects Committee (IRB) PSF 2/23/15

Page 23 of 37

IRB# 2012-1826-F PI: [name] 1. Drug-free interval

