Official Title: PET and MRI Brain Imaging of Bipolar Disorder

NCT: NCT01880957

Document Date: 11/14/2017

Proposed Statistical Plan for [11C]-DASB (5-HTT) & [11C]-CUMI-101 (5-HT1A) from [name] **Bipolar Study**

Outcomes

DASB: V_T/f_p + bootstrap ROI error

CUMI: BP_F + bootstrap ROI error (BP_{ND}??)

A priori ROIs

DASB: acn, amy, midbrain, gcirc

CUMI: acn, amy, cin, dlPFC, parahippocampal gyrus, hippocampus, raphe

Statistical methods:

Linear mixed models with subject fit as random variable LMM also with DASB & CUMI reference regions and fp

Key outcomes: p-values for main effects/interactions; overall model R² & p-value; standardized & unstandardized β's, 95% CIs, p-values for post-hocs

Covariates

DASB: age

CUMI: age, sex, previous med status (dichotomous – w/n 4 years)

Post-Treatment

Sample: HC, pre BPD, post BPD

Question 1: Do post-treatment BPD levels of DASB or CUMI differ from pre-treatment levels and HCs?

Interactions of interest:

Group (relationship btw brain & Group across all regions) **Group*ROI** (ROI-specific relationship btw brain & Group)

Treatment Effects

Sample: pre/post BPD pairs

Tx response: % change in HDRS-24 (continuous) and remitter/non-remitter (dichotomous)

Question 2: Is the % change in DASB or CUMI associated with the treatment outcome?

Interactions of interest:

AHDRS (relationship btw brain & Tx outcome across all regions) **ΔHDRS*ROI** (ROI-specific relationship btw brain & Tx outcome)

Dichotomous

Interactions of interest:

Remission (relationship btw brain & Tx outcome across all regions)

Predicting Treatment Outcome

Sample: pre BPD with pre HDRS-24 + >7-week HDRS-24

Tx response: % change in HDRS-24 (continuous) and remitter/non-remitter (dichotomous) (responder ??)

Question 3: Do pre DASB or CUMI in any of the *a prioris* predict treatment response? Are the *a prioris* independent predictors of treatment response?

Interactions of interest:

PET roi (pre-treatment PET in ROI predicts treatment response)

Interactions of interest:

PET_roi (any significant ROIs are independent predictors of Tx response (over and above the other ROIs))

Same models fit with dichotomous remission status

Additional question: Do pre DASB & CUMI together predict more of the variance in treatment response than either method alone?

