Change in overall model R² from models with pre DASB & CUMI alone to combined model (If R² increases with both methods, tracers are predicting unique properties of Tx response)

Question 4: With what accuracy does pre DASB or CUMI predict treatment response?

Penalized logistic regression models

Additional question: With what accuracy do pre DASB & CUMI together predict treatment response Metrics of interest:

Accuracy, AUC, sensitivity, specificity, NPV, PPV, model factor importance ranking or % of variance explained with each factor

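### SAP Question 4 lists a regional importance ranking from at most 38 patients with no measure of its stability; bootstrap it, label it exploratory, and drop the per-factor variance metric

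*SAP*

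**What the plan says.** Question 4 of the SAP asks how accurately pre-treatment DASB or CUMI, alone or together, predicts treatment response. The method is given as "Penalized logistic regression models". The metrics are accuracy, AUC, sensitivity, specificity, NPV and PPV, and last "model factor importance ranking or % of variance explained with each factor". No penalty type, tuning, resampling or definition of importance is stated. The only bootstrap in the SAP belongs to the PET outcome measures (ROI error), not to the ranking.

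The candidate regions are listed under A priori ROIs: "DASB: acn, amy, midbrain, gcirc" and "CUMI: acn, amy, cin, dlPFC, parahippocampal gyrus, hippocampus, raphe". That is 4 and 7 regions, or 11 in a combined model.

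The Protocol's Study Sample section sets the ceiling on patients: "Total subjects: N = 86 (38 bipolar, 38 healthy volunteer, 10 unipolar". The prediction sample is narrower: "pre BPD with pre HDRS-24 + >7-week HDRS-24". For a combined model it can shrink again, because under PET Studies "Participants may have only one of these scans, depending on radiotracer availability".

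**The concern.** A ranking invites a regional conclusion, namely that one named region is the key predictor of response. With few patients the order of fitted coefficients carries a lot of sampling noise. When regions share between-subject variation, the penalty also divides or reassigns the shared signal among them partly by chance. Good cross-validated accuracy does not cure this, since a model can predict equally well while crediting a neighbouring region. Without a stability measure, a reader cannot tell a firm first place from a near tie.

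The alternative metric has its own difficulty. Correlated predictors have no unique split of explained variance, and a logistic model has no single definition of variance explained to begin with.

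**Working it through.** **The plan's own figure.** None is given for Question 4. The 38 comes from the Power Analyses section, which sizes the bipolar-control comparison. A two-group approximation from the preliminary 5-HTT result (F = 5.41, 18 vs 41 subjects) gives d = √5.41 × √(1/18 + 1/41) = 2.326 × 0.2828 = 0.658. With 38 per group, 0.658 × √(38/2) − 1.96 = 0.91, or about 82% power, against the stated 80%. So 38 is coherent for that comparison. It was not chosen for ranking regions.

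**Inputs.**
- From the documents: N = 38; 7 CUMI regions, 4 DASB regions.
- Assumed, because the documents give no values: equal pairwise correlation of 0, 0.5, 0.7 or 0.9; remission 40% (0.40 × 38 ≈ 15 remitters); one truly predictive region with odds ratio 2 or 3 per SD; importance taken as absolute standardised coefficient. The SAP's covariates were not modelled.

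**Is correlation plausible?** The SAP's DASB outcome is V_T/f_p. Protocol Table 2 defines BP as (V_T − V_REF)/f_1, with f_1 the plasma free fraction; reading the SAP's BP_F as this quantity, every CUMI region in a subject shares one divisor and one subtracted reference. Error in those shared terms moves all regions together. If the SAP's open alternative, BP_ND, is chosen, the shared divisor goes but the shared reference remains. The likely direction is positive; the size is unknown.

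**Wrong region ranked first, N = 38, 7 CUMI regions, one true predictor.**

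| Correlation | Ridge, odds ratio 3 to 2 | Lasso and ridge, penalty tuned by 5-fold CV |
|---|---|---|
| 0 | 16-41% | 9-41% |
| 0.5 | 30-55% | 23-50% |
| 0.7 | 40-68% | 38-60% |
| 0.9 | 62-78% | 60-73% |

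Pure chance would be wrong in 6/7 = 86%. The tuned runs used about 500-600 data sets per setting, and lasso results are conditional on at least one region being selected. Lasso selected none in 12-42% of data sets at correlation 0.7-0.9, across the region sets studied.

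**Other settings (tuned runs).**
- 4 DASB regions: wrong in 28-50% at correlation 0.7 and 47-63% at 0.9.
- All 11 regions, with correlation 0.3 between tracers: 34-61% and 51-68%.
- Remission of 25% or 50% (11 regions, correlation 0.7, odds ratio 2): 49-64%.
- Low-N scenario: the Protocol plans lithium power by "Assuming 50% of the subjects complete the lithium treatment and repeat scans", or 0.5 × 38 = 19. With 7 CUMI regions and correlation 0.7-0.9, wrong in 54-78%. This is pessimistic, because prediction needs only a baseline scan and a late HDRS-24.

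**Would a second study name the same region?** If the true region is first with probability h and the other six are exchangeable, agreement = h² + (1 − h)²/6. For tuned ridge at correlation 0.7 and odds ratio 2, h = 0.401: 0.161 + 0.359/6 = 0.22. At odds ratio 3, h = 0.598: 0.358 + 0.162/6 = 0.38. At correlation 0.9, h = 0.275 and 0.382 give 0.16 and 0.21. Chance is 1/7 = 0.14.

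**Variance per factor.** Take two standardised predictors with equal coefficient 1 and correlation 0.7, on a linear scale for simplicity. Explained variance is 2 × (1 + 0.7) = 3.40. The predictor entered first receives (1 + 0.7)² = 2.89 (85%) and the second 1 − 0.7² = 0.51 (15%). Reversing the order reverses the shares, although the two are equally important.

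**The case against.** The strongest reply is that the premise of high correlation is not in the documents. The nearest text, in section C.1, says the group deficit did not differ across regions, which is not a between-subject correlation. At correlation 0.5 or below with odds ratio 3, the tuned runs (4, 7 or 11 regions) rank the true region first in about 69-93% of studies. This stands: the size depends on unstated inputs. It does not remove the point, since even at zero correlation the wrong-first rate for 7 regions reaches 41% with odds ratio 2.

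Second, the ranking is the last of several metrics and is joined by an or, so it may never be produced; accuracy and AUC answer the question asked. This also stands, and it limits the weight of the point.

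A reader might infer more than the documents support:
- *That the ranking would not reproduce.* Across the 4-, 7- and 11-region runs at correlation 0.7-0.9, two studies agree on the top region in 16-55%, against 9-25% by chance. That is weak agreement, but it is above chance. If all seven regions predicted equally, agreement of 1 in 7 would hold at any sample size and says nothing about 38 patients.
- *That the SAP commits to one ranking from one fit, ordered by coefficient size.* It is silent on both.
- *That tracer-level importance is missing.* Question 3 compares R² of single-tracer and combined models, and Question 4 lists accuracy and AUC for each tracer and for both together.
- *That no region should be named unless its rank interval excludes all others.* This is a debatable trade-off. Even a milder rule, first in at least 80% of resamples, names a region in only 3-21% of simulated studies.

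**Conclusion.** The point holds as a cheap improvement. The SAP offers a regional ranking from at most 38 patients without any indication of its stability. Under the stated assumptions the top-ranked CUMI region is wrong in roughly one trial in six to two in five with uncorrelated regions, and in about 40-78% at correlation 0.7-0.9. These figures rest on an assumed effect, remission rate, correlation pattern and importance measure, and no single value should be quoted as the trial's error rate. Dropping variance explained per factor does not depend on the simulation. The predictive-accuracy part of Question 4 is untouched.

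**What to change.** In SAP Question 4:
1. State how importance is measured, then bootstrap the whole fit including penalty tuning, for example with 1000 resamples. Keep copies of the same patient in one tuning fold, and count lasso resamples that select no region as such.
2. For each region report how often it ranks first and a 95% rank interval.
3. Label the regional ranking exploratory.
4. Delete variance explained with each factor for these models.

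No new tracer-level output is needed.

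An illustration of what this would show: with ridge, 38 patients, 7 CUMI regions, correlation 0.5-0.9 and 100 resamples, the leading region is first in a median of 42-55% of resamples, and 3-5 regions are needed to cover 90% of first places. The bootstrap reports the uncertainty and does not remove it. With all 11 regions at correlation 0.7, about 80% correct first ranks would need roughly 76 patients (odds ratio 3) to 150 (odds ratio 2).

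The cost is a few lines of SAP text and a loop around a model already planned. The downside is that regional claims become harder to make.
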